from the study. Information will be collected on serum creatinine levels, urea, eGFR, rejection episodes, graft loss/re-transplant, malignancies, opportunistic infections, patient survival and immunosuppressive therapy.

Subjects who did not complete the planned Thymoglobulin® course will be followed for any SAE(s) occurring within 30 days following the last dose of Thymoglobulin®. **These SAE(s) will be reported on the (MedWatch SAE Form) and UPLOADED to the Sanofi PV Portal, and faxed to Cleveland Clinic PI – “Attention: [name]” at [contact], within 24 hours of Study Site discovery/notification.** Since subjects will be followed even after discontinuation of the Study Drug, the **Study Completion CRF** should only be completed at 30 days, and Month 12 or earlier if the subject can no longer be followed. The following reasons are potential causes for premature discontinuation of study: graft loss, death, lost to follow-up and withdrawal of consent.

I. Emergency Un-Blinding of Treatment Assignment

This is an open-label study.

J. Study Completion and Post-Study Treatment

A Study Completion CRF should be completed at Month 12. The Investigator also must provide follow-up medical care for all patients who are prematurely withdrawn from the study, or must refer them for appropriate ongoing care. In addition, investigators will be asked to provide, for each randomized patient, a one-year follow-up data to describe patient survival, graft survival, acute rejection, current immunosuppressive regimen, recurrence of hepatitis C and renal function.

EFFICACY AND SAFETY ASSESSMENTS:

A. Renal function

Renal function will be assessed by estimated Glomerular Filtration Rate (eGFR), using the MDRD 4-variable equation. Serum creatinine will also be used as a parameter for determination of renal function at each Study Visit. Subjects will be classified for each occurrence of AKI according to the criteria in **Table 2**. Serum creatinine and weight must be recorded on the Study Visit CRF. All subjects will have their eGFR assessed at baseline, **Month 1, 3, 6, 9 and Month 12 post-transplant.**

B. Acute Cellular Rejection

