Each Study Site will report Adverse Events / Serious Adverse Events to the respective Study Site IRB in accordance with each Study Site’s, IRB Reporting Policy.

STUDY ASSESSMENTS:

A. Visit Schedule and Assessments

Study subjects will be seen and evaluated according to the **Study Visit/Assessment Schedule, [Appendix A]**. A Visit Window of [± 3 days] should be maintained for [**Visits 11 and 12 (Months 1 and 3)**]. A Visit Window of [± 7 days] should be maintained for [**Visits 13-15 (Months 6, 9, and 12)**]. Whenever possible, effort should be made to ensure that all Study Visits are timed to coincide with regularly scheduled post-transplant follow-up visits. Additional clinic visits may be made according to the subject’s status and the routine practice at the Investigative Study Site.

B. Physical Examination:

A limited physical examination/assessment will be performed at all study visits. Information about the physical examination must be present in the source documentation at the study site. Significant findings that are present prior to the start of study drug are to be recorded as part of the patient’s Relevant Medical History/Current Medical Conditions, and recorded on the appropriate CRF. Significant findings made after randomization, which meet the definition of an Adverse Event, are to be recorded as an AE or SAE, and recorded on the appropriate CRF.

C. Vital Signs:

Vital signs include measurements of Height (only at baseline); Body Weight; Pulse (while sitting or lying); and Systolic/Diastolic Blood Pressure(s). The results will be recorded on the appropriate CRF.

D. Laboratory Evaluations:

The following laboratory studies are to be performed at the time points as stated below and on the Study Visit Calendar. In addition, laboratory studies should be performed consistent with Standard of Care for the Liver Transplant Program at each respective Study Site. Blood samples will be collected in a fasting state, **(if possible)**. All patients with laboratory tests containing clinically significant abnormal values are to be followed until the values return to normal ranges or until a valid reason, (other than drug related AE), is identified.

Patients who are withdrawn “early” from the study will continue to have labs monitored as part of their routine post liver transplant follow-up per each study site post liver transplant protocol.

Hematology:

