To include: Hemoglobin, WBC, differential count and platelet count. **[Day (-1) or 0 [Pre-OLT]; Month(s) 1, 3, 6, 9, and 12.**

Blood Chemistry:

Albumin, sodium, potassium, calcium, inorganic phosphate, chloride, urea, creatinine, glucose, AST, ALT, alkaline phosphatase, total bilirubin. **[Day (-1) or 0 [Pre-OLT]; Month(s) 1, 3, 6, 9, and 12. eGFR will be measured on all subjects Day 10, Month(s) 1, 3, 6, 9, and 12.**

Lipid Panel – [Triglycerides, Total Cholesterol, HDL Cholesterol, calculated VLDL Cholesterol, calculated LDL Cholesterol, calculated Total Cholesterol to HDL ratio, calculated LDL to HDL ratio, calculated Non HDL Cholesterol]. **Month(s) 1, 3, 6, 9, and 12.**

Viral Serology:

Viral Serology Testing is to be performed at **Baseline [Day (-1) or Day 0]**, (if **NOT** previously performed): HIV 1 and 2 antibody screen; Hepatitis B Surface Antigen, Hepatitis B Core Antibody Total, Hepatitis B Surface Antibody Qualitative; Hepatitis C Antibody. **Prior results for Viral Serology Testing may be used.** Date(s) of results are to be documented on the CRF.

Viral Load / Viral Infections (HCV, EBV, CMV, HBV):

Hepatitis C – [Hep C RNA by PCR, Quantitative]; **EBV** – [EBV by PCR Quantitative]; **CMV** – [CMV DNA detection]; **Hepatitis B Virus** – [Hep B DNA, Ultra Quantitative]. **[HCV levels (for HCV negative patients), EBV, CMV, and HBV levels to be performed per Standard of Care for the Liver Transplant Program at each respective Study Site]. Patients who are HCV positive will require HCV RNA (quantitative levels) drawn at Week 1, Month(s) 1, 3, 6, 9, and 12 in order to follow the patient’s HCV response to Thymoglobulin®.**

CNI – Trough Levels:

Tacrolimus – C-0h blood trough level(s). Therapeutic drug monitoring will include Tacrolimus C-0h blood trough levels, which will be performed per Study Site Institutional Standards. Trough levels for Tacrolimus are to be performed approximately 12 hours after the previous dose of drug. **[Month(s) 1, 3, 6, 9, and 12, and per Investigative Site Liver Transplant Protocol]**

Pregnancy Tests:

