I = Liver Biopsy to be performed as clinically indicated, (for confirmation of suspected ACR and/or HCV infection recurrence), and per Investigative Site standard liver transplant protocol. For suspected ACR, Liver Biopsy MUST be performed PRIOR to the initiation of anti-rejection therapy.

J = PT/INR on Day (-1) or Day 0 (prior to liver transplant), and post liver transplant per Investigative Site liver transplant protocol.

K = Randomization to take place within 6 hours of completion of OLT and arrival in ICU.

L = Day (-1) or 0 [Pre OLT]; Day 10, Month(s) 1, 3, 6, 9, and 12 post LT, and per Investigative Site Liver Transplant Protocol.

M = Day 10; Month(s) 1, 3, 6, 9, and 12, and per Investigative Site Liver Transplant Protocol.

N = Month(s) 1, 3, 6, 9, and 12.

O = Serum or Urine pregnancy test to be performed on Day (-1) or Day 0 (prior to OLT), on all Women of Child Bearing Potential (WOCBP). Urine pregnancy test to be performed, (at Day 10, Month 3, and Month 12) post LT Visits, on all Women of Child Bearing Potential (WOCBP).

P = All AE(s)/SAE(s) will be reported from randomization till 30 days after study completion. Any SAE occurring after patient randomization, until 30 days after the patient has stopped study participation, must be reported. In addition, for patients who are withdrawn from study participation “early”, SAEs are to be reported for up to 12 months after the date of patient randomization, if a relationship to the study is “suspected”.

R = Per Investigative Site Liver Transplant Protocol.

S = For patients who are HCV “Negative” – per Investigative Site Liver Transplant Protocol. For patients who are HCV “Positive” – HCV RNA (quantitative levels) are to be drawn on Day (-1) or Day 0 (pre-OLT), at Week 1, Month(s) 1, 3, 6, 9, and 12 (post OLT), in order to follow the patient’s HCV response to Thymoglobulin.

T = r-ATG Infusion will be administered to subjects randomized to Arm 1 ONLY, on Day 0 (after OLT) within 12 hours of arrival in ICU, on Day 2 and Day 4 Post OLT.

U = CNI blood trough levels to be performed beginning day after initial dose of CNI and as per Investigative Site Liver Transplant Protocol, (as per clinically indicated), and at Month(s) 1, 3, 6, 9, and 12 Visits.

V = In case of early discharge after liver transplant these clinic visits and clinical data can be excluded however, immunosuppressive regimen and blood work results should be collected and recorded.

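### No required creatinine falls on Days 11 to 29, when the Thymoglobulin arm starts tacrolimus, so transient AKI may be recorded less completely in that arm

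*Combined protocol and SAP*

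**What the plan says.** **Visits and CNI start.** Appendix A places study visits on Days 0 to 7, on Day 10 (±2 days) and at Month 1 (±3 days), with none between the last two. Table 1 starts tacrolimus within 48 hours in Arm 2 (early CNI) and on Day 10 in Arm 1 (Thymoglobulin, delayed CNI).

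**Creatinine days.** Efficacy and Safety Assessments, A. Renal function, says "Serum creatinine will also be used as a parameter for determination of renal function at each Study Visit" and "Serum creatinine and weight must be recorded on the Study Visit CRF". Study Assessments, D. Laboratory Evaluations, says "eGFR will be measured on all subjects Day 10, Month(s) 1, 3, 6, 9, and 12"; its chemistry list, which includes creatinine, names pre-transplant and Month 1 onward. Appendix A footnote L gives pre-transplant, then "Day 10, Month(s) 1, 3, 6, 9, and 12 post LT, and per Investigative Site Liver Transplant Protocol". The laboratory section adds that "laboratory studies should be performed consistent with Standard of Care for the Liver Transplant Program at each respective Study Site". Neither of these last two provisions sets a frequency.

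**Recording.** Footnote V covers early discharge at Visits 7 to 9 (Days 5 to 7) and says "immunosuppressive regimen and blood work results should be collected and recorded". No matching rule exists for Days 11 to 29.

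**Endpoint.** Overall Study Design makes stage 2 to 3 AKI at 30 days a primary endpoint. It does not say whether this means any episode up to Day 30 or status on that day. The renal function section says "Subjects will be classified for each occurrence of AKI according to the criteria in" Table 2, which points to the first meaning. The DSMB also reviews AKI incidence.

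**The concern.** The experimental strategy moves the start of CNI out of the period with early study visits and into one with no study visit. The protocol lists nephrotoxicity as a tacrolimus risk. An AKI episode soon after CNI start falls near a scheduled assessment in Arm 2. In Arm 1 it reaches the study data through a required creatinine only if it is still present at Month 1. Routine tests in between probably exist, but nothing obliges a site to enter them. The trial is open-label, so discretionary testing and recording could also differ by arm.

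At stake is unequal ascertainment of a primary endpoint, in the direction that favours Thymoglobulin, and an incomplete AKI count for the DSMB.

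**Working it through.** The plan has no figure of its own on this point. The sample size table rests on delta creatinine and Month 12 GFR, and no AKI rate is assumed anywhere.

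**1. Length of the gap** (Appendix A windows, Month 1 taken as Day 30)
- Nominal: 30 − 10 = 20 days.
- Shortest: 27 − 12 = 15 days. Longest: 33 − 8 = 25 days.

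**2. Required creatinines after CNI start, up to and including Month 1**

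| Text that governs | Arm 2 | Arm 1 |
|---|---|---|
| Renal function section (every visit) | 7 (Days 3, 4, 5, 6, 7, 10, Month 1) | 1 (Month 1) |
| Appendix A chemistry row as it reads in the extracted text | 3 (Days 4, 10, Month 1) | 1 |
| Footnote L fixed days only | 2 (Day 10, Month 1) | 1 |

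The Day 4 entry may be a merged cell broken in extraction. The Arm 1 Day 10 draw coincides with its first dose, so it is not counted. The imbalance survives every reading, but its size depends on which text governs.

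**3. CNI days up to Day 30**
- Arm 2: 30 − 2 = 28 days, of which 20 (20/28 = 71%) lie in the gap.
- Arm 1: 30 − 10 = 20 days, all in the gap.
- Unobserved CNI days are equal, 20 in each arm. The tacrolimus trough target for Days 10 to 30 is also the same in both arms.

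**4. Illustration with uniform onset in both arms**

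Assumptions: true CNI-related stage 2 to 3 AKI of 15% in each arm; an episode lasts L days; onset is uniform over Days 11 to 30 in Arm 1 and Days 3 to 30 in Arm 2; onsets up to Day 10 in Arm 2 are all captured; in the gap the only look is Day 30.
- Arm 1 capture = L/20.
- Arm 2 capture = (8 + L)/28.

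| L | Arm 1 records | Arm 2 records | Spurious difference |
|---|---|---|---|
| 7 days | 15% × 7/20 = 5.25% | 15% × 15/28 = 8.0% | 2.8 points |
| 10 days | 15% × 10/20 = 7.5% | 15% × 18/28 = 9.6% | 2.1 points |
| 14 days | 15% × 14/20 = 10.5% | 15% × 22/28 = 11.8% | 1.3 points |

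If instead the daily risk r on CNI is the same in both arms, each arm misses r × (20 − L), the same number, and the gap creates no false difference.

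**5. Illustration with risk soon after CNI start** (nominal days)

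Take 7-day episodes that begin 1 to 6 days after CNI start.
- Arm 2, onset Days 3 to 8: all 6 onset days meet a visit. The Day 10 draw alone catches 5 of 6; only the Day 3 onset, over by Day 9, is missed.
- Arm 1, onset Days 11 to 16: none lasts to Day 30. Even a 14-day episode starting on Day 16 ends on Day 29.

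At the same assumed 15%, Arm 2 would record 12.5% (15% × 5/6) to 15%, and Arm 1 none through required creatinines. This is an extreme case, before adverse event reporting is counted.

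**6. Effect on the test**

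Assume true AKI of 36.8% in both arms (11.1% + 25.7%, from the Irish series of 359 recipients cited in the introduction), 55 per arm and a two-sided pooled z-test. If Arm 1 misses 20% of cases and Arm 2 misses 10%, the false-positive rate is 7.2%, against 5.3% with none missed. If both miss 30%, it is 5.0%. Only the difference in capture matters.

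**The case against.** The strongest reply has four parts.

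- **The first week may be no better fixed.** Footnote L and the laboratory section name no fixed chemistry day between pre-transplant and Day 10. Daily creatinine on Days 1 to 7 rests on the renal function section alone. A reader might infer that Arm 2 is closely watched while Arm 1 is not; the documents conflict on this and do not establish it. What stands is the smaller imbalance of 2 or 3 required values against 1, and footnote V, which protects blood results on Days 5 to 7 only.
- **Arm 2 has the same gap.** A reader might infer that the losses fall mainly in Arm 1. That needs risk concentrated just after CNI start, and the documents give no time course. A spurious benefit of 4.5 to 10 points can be obtained by taking all Arm 2 episodes as captured while spreading Arm 1 onset over Days 11 to 30 (15 − 10.5 and 15 − 5.25). That applies different models to the two arms and is not supported.
- **Other routes capture AKI.** Abnormal laboratory values count as adverse events if symptomatic, clinically significant or treated. Tacrolimus dose changes go on a CRF, and the DSMB sees all SAEs. It would therefore be too strong to say that harm is hidden from the DSMB. These routes do not record AKIN stage, however, and may miss transient, untreated stage 2 AKI.
- **The endpoint may be status at Day 30.** If so, the Month 1 creatinine serves both arms alike and the gap does not touch the AKI endpoint. This is correct, and the plan does not settle it. The Day 30 creatinine and eGFR endpoints are measured at the same visit in both arms.

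**Conclusion.** The point holds in limited form, with moderate severity. No study visit, protocol-fixed creatinine or CRF capture rule covers Days 11 to 29, when Arm 1 starts tacrolimus, whereas CNI start in Arm 2 falls among the early visits. If the AKI endpoint is cumulative to Day 30, transient AKI after CNI start can be under-recorded more in Arm 1, and the error favours Thymoglobulin.

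The size cannot be known from the documents. It is about 1.3 to 2.8 points with uniform onset, 7- to 14-day episodes and an assumed 15% rate in each arm. It is nil if daily risk on CNI is constant and equal, and larger if risk is front-loaded. All of these rest on assumed rates and durations, and on no routine-care value in the gap being recorded.

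**What to change.** 1. Define the primary AKI endpoint as the highest AKIN stage reached from Day 0 to Day 30, with stages 2 and 3 counted as events.
2. Require every serum creatinine drawn in routine care from Day 0 to Day 30, inpatient or outpatient, and any renal replacement therapy start date, on the CRF in both arms.
3. Use this one dataset for the primary AKI analysis and for the DSMB's AKI review.
4. Reconcile the renal function section, the laboratory section, the Appendix A chemistry row and footnote L on which days creatinine is measured.

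The cost is protocol and CRF wording, plus entry of values already in the medical record. No additional blood draw is needed for this change, and the sample size is unaffected.

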Mycophenolate mofetile	1000 mg BID start on day one post-transplant	1000 mg BID start on day one post-transplant
Corticosteroids	As per Transplant Center Immunosuppression Protocol - Taper off between 21 days-6 months post LT	As per Transplant Center Immunosuppression Protocol - Taper off between 21 days-6 months post LT

The Data Safety Monitoring Board (DSMB) will review the data on the first 30 subjects who have completed 30 days study enrollment.

Primary Endpoints:

- The incidence of AKI at 30 days post-transplant.
- Serum creatinine and eGFR at 30 days post-transplant.

Secondary Endpoints:

- The incidences of acute cellular rejection, (ACR), at 30 days post-transplant.
- Patient survival at 6 months post-transplant.
- Graft survival at 6 months post-transplant.
- The incidences of AEs and SAEs.

The primary endpoint for the study is a composite renal endpoint of Acute Kidney Injury, (**stages 2 to 3**), at 30 days post OLT. The staging of AKI will follow the classification system proposed by the Acute Kidney Injury Network (AKIN) depicted in **Table 2**.²⁶

TABLE 2: Classification / Staging for Acute Kidney Injury (AKI)

Classification/Staging System for Acute Kidney Injury ²⁶		
Stage:	Serum Creatinine Criteria	Urine Output Criteria:
1	Increase in serum creatinine of ≥ 0.3 mg/dL, (≥ 26.4 $\mu\text{mol/L}$), or an increase of $\geq 150\%$ to 200% , (1.5 to 2-fold), from baseline.	Less than 0.5 mL/kg per hour for more than 6 hours
2	Increase in serum creatinine of $> 200\%$ to 300% , (>2 to 3-fold), from baseline.	Less than 0.5 mL/kg per hour for more than 12 hours
3 ^a	Increase in serum creatinine to more than 300% , (>3 -fold), from baseline, (or serum creatinine of ≥ 4 mg/dL, [≥ 354 μmol], with an acute increase of ≥ 0.5 mg/dL, [44 $\mu\text{mol/L}$].	Less than 0.3 mL/kg per hour for 24 hours, or anuria for 12 hours.

^aOnly **one criterion** (creatinine or urine output) must be fulfilled to qualify for a stage. Individuals receiving renal replacement therapy (RRT) are considered to have met the criteria for **Stage 3** irrespective of the stage they were in at the time of RRT.

B. Patient Population

Study participants will be recruited from the Liver Transplant Programs at Cleveland Clinic, Cleveland, Ohio; University of Cincinnati, Cincinnati, Ohio; Medical College of Wisconsin Milwaukee, Wisconsin, and Cleveland Clinic Weston, Florida

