Acute cellular rejection (ACR) will be assessed using the **Banff Criteria** for rejection. All acute rejection episodes will require biopsy confirmation. Acute rejection will be defined as any biopsy-proven **Grade 1 (mild) or higher rejection using the Banff Criteria**. Biopsy results, (as graded by the local pathologist at each respective Study Site), will be recorded on the Liver Allograft Biopsy CRF using a standard liver biopsy grading procedure, for both Acute and Chronic Rejection. **In addition, all episodes of ACR will be considered an Adverse Event, (AE), and an AE (MedWatch) Form must be completed.**

Therapy for biopsy-proven acute rejection (BPAR) will be administered according to Study Site Institutional Standards.

C. Graft loss

The allograft will be presumed to be lost if a patient has a liver re-transplant, or in the event of patient death. In the event of Graft Loss, an **SAE (MedWatch) Form must be completed and UPLOADED to the Sanofi PV Portal, and faxed to Cleveland Clinic PI – “Attention: [name]” at [contact]**, within 24 hours of Study Site discovery/notification. The reason for graft loss will be recorded on the Graft Loss CRF and on the Study Completion CRF.

D. Death

In the event of patient death, an **SAE (MedWatch) Form must be completed and UPLOADED to the Sanofi PV Portal, and faxed to Cleveland Clinic PI – “Attention: [name]” at [contact]**, within 24 hours of Study Site discovery/notification. The events leading to the death must be entered on the AE/SAE CRF and on the Study Completion CRF.

E. Safety

Adverse Events and Serious Adverse Events (AEs/SAEs)

THYMOGLOBULIN® – Rabbit Thymocyte Globulin (r-ATG):

The most common systemic Adverse Events occurring during and after Thymoglobulin® Infusion are:

- Fever (63%)
- Chills (57%)
- Pain (46%)
- Headache (40%)
- Abdominal pain (38%)
- Diarrhea (37%)
- Hypertension (37%)
- Nausea (37%)
- Peripheral Edema (34%)
- Dyspnea (28%)
- Asthenia (27%)
- Hyperkalemia (27%)
- Tachycardia (27%)

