Persistent or significant disability/incapacity: A substantial disruption of a person's ability to conduct normal life functions.

Important medical events: Medical and scientific judgment should be exercised in deciding whether expedited reporting is appropriate in other situations such as important medical events which may not be immediately life-threatening or result in death or hospitalization, but might jeopardize the patient or may require intervention to prevent any of the other outcomes listed in the definition of a Serious Adverse Event. These should also be considered Serious Adverse Events.

In addition, all biopsy confirmed reports of acute cellular rejection (ACR) will be submitted to Sanofi PV as an SAE whether or not the event has met the SAE criteria. Since acute cellular rejection (ACR) is a secondary endpoint of the study, all BPAR episodes are to be reported through the Sanofi PV procedures, for consistency and accuracy in event reporting and data analysis. The event is to be noted with an SAE criterion of “**Other Important Medical Event**”.

Any SAE occurring after patient randomization, until 30 days after the patient has stopped study participation, must be reported. In addition, for patients who are withdrawn from

study participation “early”, SAEs are to be reported for up to 12 months after the date of patient randomization, if a relationship to the study is “suspected”.

Information about all SAEs will be collected and recorded on the SAE (MedWatch) Form. **To ensure patient safety, the SAE (MedWatch) Form must be completed and UPLOADED to the Sanofi PV Portal, and faxed to Cleveland Clinic PI – “Attention: [name]” at [contact], within 24 hours of Study Site discovery/notification.**

C. Pregnancies

Any female subject who becomes pregnant after the initiation of study treatment will be discontinued from further study treatment and participation. The patient will continue to be treated per standard treatment as per the Study Site standard practice. Any pregnancy occurring while the patient is participating in the study, (and for up to 30 days after study participation), is to be reported to Sanofi PV within 24 hours of learning of the occurrence. **For all pregnancies, a MedWatch SAE Form will be completed and UPLOADED to the Sanofi PV Portal, and faxed to Cleveland Clinic PI – “Attention: [name]” at [contact], within 24 hours of discovery/notification.**

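### The pooled SAE incidence counts every biopsy-proven rejection, serious or not, so it partly repeats the rejection endpoint and can blur the safety contrast in either direction

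*Combined protocol and SAP*

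**What the plan says.** Under Adverse Event and Serious Adverse Event Reporting, part B, every biopsy-confirmed acute cellular rejection (ACR) "will be submitted to Sanofi PV as an SAE whether or not the event has met the SAE criteria". The same paragraph ties the rule to ACR being a secondary endpoint and gives its purpose as "for consistency and accuracy in event reporting and data analysis". On coding it says "The event is to be noted with an SAE criterion of" Other Important Medical Event, which is one of the ordinary seriousness categories in that section.

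Efficacy and Safety Assessments, part B, sets the threshold for rejection at "Grade 1 (mild) or higher rejection using the Banff Criteria". It then says that "all episodes of ACR will be considered an Adverse Event, (AE), and an AE (MedWatch) Form must be completed".

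The secondary endpoints under Overall Study Design include "The incidences of acute cellular rejection, (ACR), at 30 days post-transplant" and, as a separate item, "The incidences of AEs and SAEs". Study Endpoints / Efficacy and Safety, part B, repeats both. Part C adds biopsy-proven rejection at 6 and 12 months and AEs and SAEs at 12 months. No section says that rejection filed only under the blanket rule is left out of the SAE count, and no SAE summary without rejection is planned.

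**The concern.** An SAE rate is normally read as the share of patients with an event that met a seriousness criterion. Here it also includes patients whose only qualifying event was a mild, non-serious rejection. Two secondary endpoints then share events, and a difference in rejection between arms carries over into the SAE figures.

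This matters because the safety question is whether induction brings more infections, cytopenias or infusion reactions. If the control arm has more rejection, the rule adds more patients to the control SAE count and the pooled line understates any such excess. If the delayed-CNI arm has more rejection, the pooled line overstates it. In neither case does the headline figure measure seriousness alone.

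**Working it through.** **Plan's own figure.** There is none on this point: the documents state no expected SAE rate and no overlap with rejection. The sample size of 110 was set for creatinine change and does not bear on it.

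**Inputs.**
- h = proportion with any SAE other than rejection. Assumed: 20% control, 35% Arm 1, a 15-point excess.
- r = proportion with biopsy-proven rejection. The cited randomised steroid-elimination study gives 32% control and 20.5% Thymoglobulin. The cited retrospective series of 298 patients gives one-year freedom from rejection of 50% and 72%, so r = 50% and 28%. Neither is described as withholding CNI for 10 days.
- Two further cases: equal rejection (20% each, assumed), and the 30% and 17% of the cited living-donor series with the arms swapped, to represent more rejection in Arm 1.
- f = share of rejections that meet no ordinary seriousness criterion. Not in the documents; 1, 0.5 and 0 are shown.
- Rejection and other SAEs are taken as independent within a patient.

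**Formulas.**
- As filed: 1 − (1 − h)(1 − r)
- By the ordinary criteria: 1 − (1 − h)(1 − r(1 − f))

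**Worked case, r = 32% and 20.5%.**
- As filed: control 1 − 0.80 × 0.68 = 45.6%; Arm 1 1 − 0.65 × 0.795 = 48.3%; difference +2.7 points.
- Ordinary criteria, f = 1: 20.0% and 35.0%; +15.0 points.
- Ordinary criteria, f = 0.5: control 1 − 0.80 × 0.84 = 32.8%; Arm 1 1 − 0.65 × 0.8975 = 41.7%; +8.9 points.
- f = 0: same as filed, so the rule changes nothing.

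**All cases (Arm 1 minus control, points).**

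| Rejection, control vs Arm 1 | Ordinary criteria, f = 1 | Ordinary criteria, f = 0.5 | As filed |
|---|---|---|---|
| 32% vs 20.5% | +15.0 | +8.9 | +2.7 |
| 50% vs 28% | +15.0 | +4.1 | −6.8 |
| 20% vs 20% | +15.0 | +13.5 | +12.0 |
| 17% vs 30% | +15.0 | +18.0 | +20.9 |

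**Sensitivity.**
- With h = 40% and 55% and r = 32% and 20.5%, the as-filed difference is (1 − 0.45 × 0.795) − (1 − 0.60 × 0.68) = 64.2% − 59.2% = +5.0 points.
- With a smaller excess, h = 35% and 40%, it is 52.3% − 55.8% = −3.5 points. By the ordinary criteria it is +5.0 at f = 1 but only 46.15% − 45.4% = +0.75 at f = 0.5.
- The randomised study's printed counts, 7/33 and 11/33, are 21.2% and 33.3%. Using these, the first case becomes 48.8% − 46.7% = +2.1 points.

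**Precision.** With 55 per arm and rates of 20% and 35%, the 95% half-width is 1.96 × √(0.20 × 0.80/55 + 0.35 × 0.65/55) = 16.5 points. Chance variation alone is larger than most of these shifts.

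**The case against.** A reader might infer that the plan tests SAE incidence between arms and that the rule will reverse the result. The documents do not support that. The secondary objectives speak of comparing survival between groups, but for AEs and SAEs only of determining incidence in each group. The Z-based confidence interval is specified for efficacy events. No SAE test or decision rule is stated.

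A reader might also infer that harm would be hidden from view. It would not be. AEs are summarised by body system, severity and causality and listed by patient with preferred term. Infections are analysed separately and tabulated by type and organism. Rates of notable laboratory abnormalities are given by treatment. Infusion reactions go on the AE form. The DSMB reviews ACR and SAEs as separate items.

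Nor is the direction settled. The effect of the delay on rejection is an open secondary objective, and in the cited pilot rejection was higher in the low-dose Thymoglobulin group. Many early rejections may also be serious anyway, through prolonged hospitalisation or as important medical events. The lower Arm 1 rate would then be partly or wholly real.

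Finally, the AE wording in one section and the SAE wording in the other need not conflict, since every SAE is also an AE. The mismatch is one of form and label.

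All of this stands and narrows the point to the pooled SAE line. It does not remove the point: that line is a named secondary endpoint, and the plan does not say whether non-serious rejection belongs in it.

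**Conclusion.** The point holds for the pooled SAE incidence. As written, non-serious rejections count as SAEs and the figure partly repeats the ACR endpoint. Any difference in rejection between arms then distorts the SAE contrast, towards masking a Thymoglobulin excess if rejection is lower in Arm 1 and towards exaggerating it if higher.

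The size cannot be fixed from the documents. At the randomised study's rejection rates and the assumed 20% and 35%, the rule removes 12.3 points of apparent excess if no rejection is otherwise serious (15.0 to 2.7), 6.1 if half are, and none if all are. A change of sign needs a larger rejection difference or a smaller true excess. These figures rest on assumed SAE rates, independence, and rejection rates from studies of other designs. This is a modest, inexpensive improvement to one secondary safety summary; it does not threaten the primary analysis, and no data are lost.

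**What to change.** Leave the pharmacovigilance submission rule as it is. In Study Endpoints / Efficacy and Safety (Secondary Endpoints, and the Adverse Events / Infections paragraphs), report SAE incidence by arm in three ways:

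1. all SAEs as filed;
2. excluding all biopsy-proven rejection, identified by preferred term, which needs no new data;
3. by the ordinary seriousness criteria, excluding only rejection that met none of them.

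State in advance which of the three is the secondary endpoint.

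The third line cannot be built from the SAE criterion on the form. The reporting section assigns the Other Important Medical Event code to all these rejections without limiting it to the non-serious ones, so dropping events by that code could discard truly serious rejection. Add one CRF item recording whether each biopsy-proven rejection independently met an ordinary criterion.

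Align the form and classification wording in the Acute Cellular Rejection section ("all episodes of ACR will be considered an Adverse Event") with the SAE section.

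Cost: one CRF field and two extra table lines.
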